This is a before and after methodological approach, which will involve collection of baseline data over 12 months, followed by staged implementation. Implementation will take place over two phases: a sandbox, or virtual implementation of the system (referral decisions made by GDPs will be captured, however all patients will ultimately be treated in secondary care) followed by full implementation of the system, (appropriately referred patients being treated in both primary and secondary care settings).

The pilot study suggests that changes in referral behaviour can be detected as early as three months following the introduction of a management system. The cost reductions seen by triage diversion are seen immediately. However, in order to understand the long-term implications of the referral system, including any reactive behaviour by GDPs or Secondary Care providers we are proposing to run the introduction of the system for 12 months and the full diversion service for a further 12 months. This should allow a full financial year's worth of cost data to be assessed as well as determining the degree of adaptation to the system. The time period will also enable a robust assessment of primary care treatment quality – i.e. there will be sufficient time to determine if cases treated in primary care return to secondary care for additional or remedial treatment as well as tracking seasonal variations in

Version 2 15 September 2015

referrals. For example we have noted decreases in referral volumes around December and January (relating to the holiday period) and increases in volumes round March (relating to end of financial year).

Implementation 1: Virtual Referral management without diversion (year 2)

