There is evidence to suggest that the process of collecting, assessing and administratively triaging referrals can result in a decrease of referrals into secondary care. The first twelve months of the intervention will therefore involve practitioners using the electronic referral system, the conditional entry process and the use of administrative and clinical triage. Although the system will capture the decision-making, no primary care diversion will be available and all patients will ultimately be seen in secondary care settings. Referrals that do not meet the threshold will be returned and the case notes system will be in operation enabling advice to be given and further information to be sourced. The system will therefore be operational, but patients will not be diverted to alternate providers. Data from this phase of the study will be used to assess primary care MOS need and applied to assist the procurement of appropriate services based on an AQP (any qualified provider) approach in preparation for the full implementation of the system. In addition, data from this phase will be used to assess the potential activity loss from the acute trust providers.

Implementation 2: Full Referral management with diversion (year 3)

The system will be fully operational and implemented with the use of primary care MOS services.

Outcomes

The primary outcome will be the number and ultimate destination of referrals: rejected, primary care, primary advances or secondary care. There are three main sources of data that will be collected:

- a) Referrals entering acute trusts from dentists via the referral receipt centre of the relevant hospitals
- b) NHS monitoring data received by the local Primary Care Trust and the Payment by Results system including tariff charges associated with this type of activity
- c) Reporting data from NHS business services authority on referrals made by practitioners

This data will be collected continuously, throughout the duration of the study.

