For the minority of Sefton patients who chose to attend a secondary care clinic other than Ormskirk District General, patient information sheets and consent forms will be sent to participants direct from the referral capture centre following receipt of their referral, with stamped addressed envelopes enclosed to facilitate the return of consent forms. Following receipt of consent forms, participants will be sent questionnaires designed to collect baseline data, in time to coincide with their oral surgery consultation appointment. These questionnaires are to be completed after the consultation has taken place, so that patients will have an accurate idea of costs incurred. This system is required as some clinics have low number of eligible patients and hence cannot be staffed viably by CRN personnel. The ability for potential participants to ask questions of the research team is facilitated by the provision of telephone and email contact information.

Participants will be offered a gift voucher to the value of £10 to be redeemed with Amazon or a similar retailer on receipt of their questionnaire. This is to thank them for to completing the questionnaire and take part in the study.

Professionals

NHS commissioners, Acute Trust Staff and General Dental Practitioners will be approached by a member of the research team, either by telephone or face to face during the course of the study. Consent will be sought from these professionals prior to taking part in any interviews or focus groups.

Version 2 15 September 2015

C. Monitoring of the study

This study will be monitored by Staff from the University of Manchester Dental Health Unit, at periodic intervals by the principle investigator and consultants to ensure that the study is being conducted according to Good Clinical Practice Guidelines. NHS guidelines regarding 18 week waiting times will be adhered to.

G. Randomization

No randomisation necessary, a census approach will be adopted, which encompasses all practices and acute trust providers within NHS Sefton.

H. Outputs

Referrals Method

Patients' understanding of treatment pathway

Number and ultimate destination of referrals

Data monitoring

Number and reasons for DNA appointments Data monitoring/ questionnaire/ interviews

Rejected referrals

What happened? Data monitoring/ interviews

Costs

Understanding of treatment pathway Interviews
Quality of data Data monitoring
Time of referral to appointment Data monitoring

XI. DATA ANALYSES

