Statistical analysis will be undertaken using time series regression models. Pre-intervention and post-intervention (virtual and actual implementation) trends will be evaluated. In addition, the pre and post intervention effects at Sefton will be compared with national trends in order to further investigate the effects of possible secular trends. Analysis and reporting will be undertaken according to recommended quality criteria (Ramsay et al, 2003). The best fit pre intervention and post intervention lines will be estimated using linear regression and autocorrelation will be adjusted for by using the maximum likelihood methods where appropriate (Draper & Smith 1981). First order autocorrelations will be tested for statistically using the Durbin – Watson statistic and higher – order autocorrelations will be investigated using the autocorrelation and partial autocorrelation function.

Two effect sizes will be estimated. First, a change in level of outcome at the first point of after the introduction of the intervention will be estimated for each of the referral outcomes (Primary Care, Secondary care, DWSPI, rejected). This will be carried out by extrapolating the pre intervention regression line to the first post intervention point. The difference between this extrapolated point and the post intervention regression estimate for the same point will represent the estimated change in level of referrals. Secondly, a change in the slopes of regression lines will be investigated by calculating the post intervention minus pre intervention slope. The difference observed for each change will be further investigated for statistical significance.

Data will also be presented descriptively and graphically on the number and nature of referrals according to the referral destinations of rejected, primary care, primary advanced or secondary care.

Version 2 15 September 2015

Any trends observed for referrals to secondary care for Sefton will be compared with national trends using Hospital Episode Statistics (HES), which will be obtained via NHS Sefton and analysed for statistical significance at each recorded time point.

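### The two planned effect sizes, a level change at the first post-change month and a slope change, do not report a sustained effect that builds up over the first months

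*Protocol*

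**What the plan says.** The Protocol's section XI, Quantitative data analysis, names two effect sizes for each referral destination.

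- Level: "First, a change in level of outcome at the first point of after the introduction of the intervention will be estimated". The pre-intervention line is extrapolated to that point, and "The difference between this extrapolated point and the post intervention regression estimate for the same point will represent the estimated change in level of referrals".
- Slope: "a change in the slopes of regression lines will be investigated by calculating the post intervention minus pre intervention slope".

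The section mentions neither a transition period nor a contrast at any later month.

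The section headed Interrupted time series study gives the timing information. In the pilot, "changes in referral behaviour can be detected as early as three months following the introduction of a management system". The next sentence says: "The cost reductions seen by triage diversion are seen immediately". To learn about long-term implications and adaptation, "we are proposing to run the introduction of the system for 12 months and the full diversion service for a further 12 months". The Quantitative data analysis section adds that monthly data should show whether an effect is maintained or fades.

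**The concern.** The phases last 12 months so that the lasting effect can be seen, yet the level change is read at month 1. A straight line through all post months cannot follow an effect that rises for a few months and then stays flat. It tilts: too low at the start, too high at the end.

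Implementation 1 has no diversion, so any fall in referral numbers there depends largely on what dentists do, and this is where a gradual onset is most plausible. Two misreadings could follow. Referral management alone might be reported as having little level effect when it has a lasting one, and the tilt might be reported as an effect still growing at the end of the year.

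A related gap is dating. One of the three data sources is "NHS monitoring data received by the local Primary Care Trust and the Payment by Results system including tariff charges associated with this type of activity". Charged activity may be dated by attendance, not by referral, and the Protocol does not say which date places a referral and its destination in a month.

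**Working it through.** The Protocol gives no figure to reproduce and no time course, so the time courses below are assumptions.

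**Inputs.** 12 monthly points per implementation phase (Interrupted time series study); a straight line by least squares, read at the first post month (Quantitative data analysis). The pre-change line is taken as known and flat, and the sustained effect is scaled to 1.

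**Formula.** For post months t = 1 to 12 the mean is 6.5 and Σ(t − 6.5)² = 143. With effect e(t) and mean ē, the slope is b = Σ(t − 6.5)e(t) / 143, and the fitted effect at month m is ē + b(m − 6.5).

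- Three-month ramp (1/3, 2/3, then 1): ē = 11/12 = 0.917; b = 5.167/143 = 0.036. Month 1: 0.917 − 5.5 × 0.0361 = 0.72. Month 12: 0.917 + 5.5 × 0.0361 = 1.12.
- Half immediate, half after three months: ē = 0.875; b = 6.75/143 = 0.047. Month 1: 0.62. Month 12: 1.13.
- Nothing for three months, then full: ē = 0.75; b = 13.5/143 = 0.094. Month 1: 0.23. Month 12: 1.27.
- Immediate: ē = 1; b = 0. Month 1 and month 12: 1.00.

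| Assumed time course | Month 1 | Month 6 | Month 12 | Spurious slope per month |
|---|---|---|---|---|
| Immediate | 1.00 | 1.00 | 1.00 | 0 |
| Three-month ramp | 0.72 | 0.90 | 1.12 | 0.036 |
| Half immediate, half after 3 months | 0.62 | 0.85 | 1.13 | 0.047 |
| Abrupt start after 3 months | 0.23 | 0.70 | 1.27 | 0.094 |

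**Refit without months 1 to 3.** All four rows become 1.00 at every month, with slope 0.

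**If a series were dated by attendance.** With an immediate effect and waits spread evenly over 0 to 18 weeks (4.14 months), the month-1 level is 0.46 and month 12 is 1.19. If every wait were 18 weeks, the figures are 0.03 and 1.28. Dropping three months does not repair that last case (0.36 at month 1, 1.17 at month 12).

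**Precision.** Assume 12 baseline points, 12 post points and independent errors with standard deviation sigma. The variance at month m, in units of sigma², is 1/12 + (m + 5.5)²/143 for the extrapolated pre line plus 1/12 + (m − 6.5)²/143 for the post line.

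- Month 1: 0.379 + 0.295 = 0.674, SE 0.82 sigma.
- Month 6: 1.008 + 0.085 = 1.093, SE 1.05 sigma.
- Month 12: 2.225 + 0.295 = 2.520, SE 1.59 sigma.

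The refit uses nine post points (mean 8, sum of squares 60), so the post-line term becomes 1/9 + (m − 8)²/60.

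- Month 6: 1.008 + 0.178 = 1.186, SE 1.09 sigma.
- Month 12: 2.225 + 0.378 = 2.603, SE 1.61 sigma.

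**The case against.** A reader might infer more than the Protocol supports, in four ways.

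- *That the plan expects behaviour to change at three months.* It reports the earliest detection in a pilot. A gradual effect from day one could also first be detectable then. The 23% case is therefore a pessimistic bound.
- *That both changes are affected alike.* The Protocol says that cost reductions from diversion are immediate, and diversion is the subject of the principal analysis. An immediate effect is recovered in full. Implementation 1 is not purely behavioural either: referrals below the threshold are returned from go-live. If 90% of the effect is immediate, the month-1 level is 0.92.
- *That the data lag by up to 18 weeks.* The Protocol says only that "NHS guidelines regarding 18 week waiting times will be adhered to". That is a waiting-time limit, not a data lag. Referrals logged at the receipt centre need not lag, and attendance dating of the charge data is possible but not stated.
- *That the plan misses the effect.* The level comes from a line through all 12 months, not from the raw first-month count, and the slope is also estimated. The effect is misallocated between the two, not lost. Graphs are planned as well.

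It is also fair to say that level plus slope is a standard pair, that transition periods are often left to an analysis plan, and that replacing the month-1 contrast by month 12 would nearly quadruple the variance (2.520/0.674 = 3.7).

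These points narrow the concern and rule out replacing the planned effect sizes. They do not remove it: the Protocol itself fixes the first effect size at the first point, and neither planned figure describes an effect that builds up and then holds.

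**Conclusion.** The point holds in a limited form. For a constant effect that is reached gradually, the month-1 level change understates the plateau (72%, 62% or 23% of it under the three delayed courses) and the fitted line overstates it at month 12 by 12% to 27%, with a slope that is an artefact. This matters mainly for Implementation 1. It does not show that the principal analysis of diversion is biased: on referral-dated data an immediate effect is recovered in full, and only a series dated by attendance or charge would blur it.

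The shares rest on the assumed time courses and on a straight-line fit to 12 post months. A non-flat pre line would change precision, not the shares. The standard errors assume 12 baseline points and independent errors; positive autocorrelation of 0.3 raises them (0.94 sigma at month 1 and 1.98 sigma at month 12 with all 12 post months).

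**What to change.** In the Quantitative data analysis section:

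1. Keep the level change and the slope change as defined.
2. Add, as prespecified effect sizes, the fitted-minus-extrapolated difference at months 6 and 12 of each phase, with intervals.
3. Add a prespecified refit that leaves the first three months after each go-live out of the post line, and report the same contrasts from it. This matters because later contrasts from the single line are still off the plateau under delay (0.70 to 0.90 at month 6, 1.12 to 1.27 at month 12).
4. Assign each referral and its ultimate destination to the month of referral wherever the source carries that date, and state the dating rule for any source that does not.

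No new data collection is needed for items 2 and 3; item 4 depends on what each source holds. The price is wider intervals: in the refit, SE about 1.09 sigma at month 6 and 1.61 sigma at month 12, against 0.82 sigma for the month-1 contrast. The refit also does not use a full seasonal year, which the Protocol gives as one reason for the phase length, so it should stand beside the full-phase fit and not replace it.

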The quantitative analysis has been designed to evaluate the impact of a change in service, with the primary analysis using a piecewise regression / interrupted time series analysis (ITS) design. This is an appropriate methodology to evaluate the effects of a change in service delivery. Whilst it is acknowledged that the lack of a concurrent control group can be considered a weakness (Brown & Lilford, 2008), the nature of the investigation and implementation precludes such a design. The proposed study design and analysis will aim to minimize threats to internal validity (Ramsay et al, 2003): A single PCT boundary (NHS Sefton) with a diverse practice and patient profile has been identified for study; lengthy evaluation pre-intervention and during two stage implementation over three years will address any concerns regarding secular trends (Brown & Lilford, 2009). Additionally, trends observed in Sefton over the implementation period with be compared with national trends in oral surgery referrals through the examination of Hospital Episode Statistics (HES) data. This design will enable 24 months of referral management assessment during the study, and thus captures and enables the measurement of seasonal variations in referral patterns. Further, a large intervention effect has been observed in an earlier pilot study, with a re-direction of MOS referrals from secondary care to primary care based services of over 68% (data from Central Manchester Foundation Trust). The primary outcome measures will be the monthly reported number and ultimate destination of referrals from baseline through to six months, implementation stage 1 referral management alone (12 to 24 months) and Implementation stage 2, referral management with diversion (24 to 36 months). Analysing monthly data has a number of advantages: it enables the cyclical nature of referrals observed in the pilot study to be accounted for; will illustrate whether referral management alone (the process of collecting, assessing and administratively triaging referrals in the absence of diversion) results in a decrease in referrals into secondary care; short-term changes will not be missed; any observed effect is maintained or return returns to original levels. The principal analysis will be to determine whether the implementation of the Referral Management System with diversion has an effect that is significantly different from any underlying secular trend.

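### The level and slope changes are defined at a single introduction of the intervention, so none is defined at the start of diversion, which is the principal question

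*Protocol*

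**What the plan says.** The Protocol stages the intervention. After "collection of baseline data over 12 months" comes a year of referral management with no primary care diversion, then a year with diversion. Section XI (Quantitative data analysis) gives the two stages as 12 to 24 and 24 to 36 months.

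The same section fixes the main question on the second stage: "The principal analysis will be to determine whether the implementation of the Referral Management System with diversion has an effect" that differs from the secular trend. It also wants the monthly data to show whether referral management alone lowers referrals into secondary care.

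The effect definitions follow: "Two effect sizes will be estimated". The first is a level change: "a change in level of outcome at the first point of after the introduction of the intervention will be estimated", obtained by "extrapolating the pre intervention regression line to the first post intervention point" and comparing the result with the post-intervention estimate at that point. The second is a slope change, found by "calculating the post intervention minus pre intervention slope".

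Two statements bear on where this single introduction lies. Section IX, under Implementation 1, says: "The first twelve months of the intervention will therefore involve practitioners using the electronic referral system". Section XI says: "Pre-intervention and post-intervention (virtual and actual implementation) trends will be evaluated".

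**The concern.** There are two switches but one defined break. The virtual year is the start of the intervention, and post-intervention covers both years, so the first post-intervention point is the first month of Implementation 1. The principal question is about what happens a year later. At that later start no level change, slope change or comparator is defined.

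The staged design exists to separate the effect of managing referrals from the effect of diverting them. An analyst who follows the effect definitions literally measures the level change before diversion can act and absorbs the diversion step into a slope. An analyst who departs from them must choose the diversion contrast without guidance, possibly after seeing the series.

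**Working it through.** The Protocol states no figure to reproduce, so the check applies its own effect definitions to a simple series.

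**Inputs**
- Twelve monthly points per phase, taken as months 1–12, 13–24 and 25–36. The stated ranges share month 24, so 13 and 25 are inferred.
- Diversion effect: 68%, the pilot figure in section XI.
- Year-2 effect: 0%, or 9% as an illustration. The 9% is the Manchester figure in the Background; it comes from another area and covers all dental specialties.
- Flat baseline indexed to 100, no seasonality (assumption).

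**One line through months 13–36.** Number these months x = 1 to 24: mean 12.5, Sxx = 24 × (24² − 1)/12 = 1150. For a unit step halfway, Sxy = 12 × 6 = 72.
- Slope = 72/1150 = 0.0626 per month.
- Fitted value at the first point = 0.5 − 11.5 × 0.0626 = −0.22.

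A mid-period step S therefore shifts the month-13 level change by −0.22 × S and adds a slope of 0.0626 × S.

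| Year-2 fall | Months 25–36 | Step S | Pooled level change, month 13 | True | Pooled slope change per month |
|---|---|---|---|---|---|
| 0% | 32 | −68 | 0 + 0.22 × 68 = +15.0 | 0 | −4.26 |
| 9% | 32 | −59 | −9 + 0.22 × 59 = +4.0 | −9 | −3.69 |
| 9% | 0.32 × 91 = 29.12 | −61.88 | −9 + 0.22 × 61.88 = +4.6 | −9 | −3.87 |
| 15% | 0.32 × 85 = 27.2 | −57.8 | −15 + 0.22 × 57.8 = −2.3 | −15 | −3.62 |

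The true slope change is zero within every phase.

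**When the sign is wrong.** With the 68% applied to the reduced level, the pooled level change is positive when e < 0.22 × 0.68 × (1 − e), that is e < 0.1496/1.1496 = 13.0%. If referrals fall to 32 regardless, the limit is 0.1496/1.22 = 12.3%. With a diversion effect of 40% or 20% it is 0.088/1.088 = 8.1% or 0.044/1.044 = 4.2%.

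**At month 25.** The pooled line sits 0.5313 × 68 = 36.1 below baseline (true 68.0) with no year-2 effect. With a 9% fall it sits 9 + 0.5313 × 61.88 = 41.9 below (true 70.9).

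**Primary care destinations.** If these are zero until diversion and then +68, the pooled level change is −0.22 × 68 = −15.0, an impossible count.

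**Sensitivity.** With baseline growth of 1 per month and a 9% year-2 fall, the pooled level change is +8.5 (true about −10.2). With independent noise of SD 5, 10 or 15, the level estimate was positive in 92–100% of runs with no year-2 effect and in 67–89% with 9%. It was significantly positive in only 0–8%.

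**Three segments, breaks at 13 and 25.** The noise-free series is recovered exactly: 0 and −68.0 with no year-2 effect. With 9% it gives −9.0 at month 13; at month 25 it gives −61.9 against the Implementation 1 line and −70.9 against the baseline line.

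**Precision**, independent errors of SD s; each 12-point segment has Sxx = 143:
- Pooled month-13 change: √(1/12 + 6.5²/143 + 1/24 + 11.5²/1150) = √0.535 = 0.73s.
- Month-25 change against the Implementation 1 line: √(1/12 + 6.5²/143 + 1/12 + 5.5²/143) = √0.674 = 0.82s.
- Months 25–36 averaged against the extrapolated baseline: √(1/12 + 24²/143 + 1/12) = √4.195 = 2.05s.

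**The case against.** The strongest answer is that nothing in the Protocol says months 13–36 get a single line. Section XI names piecewise regression, lists the outcome in three phases and wants the effect of referral management alone, which needs its own segment. The phrase about virtual and actual trends can be read as naming two trends, and two effect sizes can mean two kinds, applied at each change. The number of segments is also something a statistical analysis plan often settles, and none is at hand here.

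Most of this stands. A reader might infer that the plan must pool the two years and cannot separate management from diversion; the text does not support that. But the Protocol is not silent on effect sizes: it fixes their kind, the extrapolation and the time point, and the three-phase reading does not reach those definitions. Even on that reading, no comparator is named for the diversion year.

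A reader might also infer that a real fall will be reported as a rise. That holds only if the years are pooled and the year-2 effect is small. The steep negative slope would be reported alongside, and the planned graphs by destination would show a 68% step.

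Finally, a reader might take the remark about incremental effects, in the section on secondary care providers, as a competing time-series contrast. It is not one: it concerns interviews and observation in the acute settings. The comparison stated for the principal analysis is with the secular trend.

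**Conclusion.** The point holds as a mismatch between the effect definitions and the principal question. On the plain reading, the level and slope changes sit at the start of Implementation 1, and none is defined at the start of diversion.

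The numerical harm depends on fitting one line to months 13–36. The month-13 level change is then wrong by 0.22 times the diversion step, in the opposite direction: +15 per 100 where the truth is 0, or +4 to +5 where it is −9. The sign is wrong only below a year-2 effect of about 12 to 13% (with 68% diversion); above that the fall is understated. These figures rest on a flat baseline, abrupt steps, the pilot's 68% and an illustrative 9%. In the noise runs a false rise was seldom significant. The firmer harm is that the diversion step is blurred into a slope and roughly 30 points of it are missing at month 25.

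**What to change.** In section XI, replace the single pre/post definition with three segments, with breaks at the start of Implementation 1 and of Implementation 2. Give the month of each break, since the stated ranges overlap at month 24. Estimate level and slope changes at both breaks for each referral outcome.

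Name in advance the contrast that answers the diversion question. Report the diversion phase in two ways: against the extrapolated baseline line (total effect against the secular trend, which matches the stated principal analysis) and against the extrapolated Implementation 1 line (the increment from diversion).

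The data and regression method stay the same. The cost is two more parameters (six instead of four) and, for the baseline contrast, real imprecision. Averaged over months 25–36 its standard error is about 2.05 residual SDs, some 2.8 times the 0.73 of the pooled month-13 change (2.05/0.73). If the residual SD were 10 per 100, the 95% half-width would be about 1.96 × 20.5 = 40. Autocorrelation and seasonality are not in these figures. The expected precision of each contrast should be stated beside its definition.

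### The only significance test named for the national HES comparison works time point by time point, which does not match the stated aim of comparing trends and pre/post effects

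*Protocol*

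**What the plan says.** All references are to the protocol, section XI (Data analyses), Quantitative data analysis, unless another place is given.

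- **Aim of the national comparison.** It is stated three times: "trends observed in Sefton over the implementation period with be compared with national trends in oral surgery referrals"; "the pre and post intervention effects at Sefton will be compared with national trends in order to further investigate the effects of possible secular trends"; and, in the closing paragraph, "Any trends observed for referrals to secondary care for Sefton will be compared with national trends using Hospital Episode Statistics (HES").
- **Test named.** The closing paragraph adds that the HES data will be "obtained via NHS Sefton and analysed for statistical significance at each recorded time point". No other significance test is attached to HES, and no model that contains the national series is described.
- **Level and slope changes.** These two effect sizes are defined from pre- and post-intervention regression lines for the referral outcomes. The definitions contain no national term. The statement that "autocorrelation will be adjusted for by using the maximum likelihood methods where appropriate" belongs to those regression lines.
- **Role of HES.** The section concedes that there is no concurrent control. It first names the long evaluation before and during the two-stage implementation as the answer to secular trends, and then adds HES.
- **Time scale.** For the Sefton series, "The primary outcome measures will be the monthly reported number and ultimate destination of referrals". The baseline is "collection of baseline data over 12 months, followed by staged implementation" (section IX, Interrupted time series study), and "This design will enable 24 months of referral management assessment during the study". The interval of the HES data is not stated.

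**The concern.** A test at a time point and a test of a difference in trend answer different questions. The first asks whether Sefton and the nation differ at that point. The second asks whether Sefton's level or slope changed at an interruption by more than the national series did. Only the second helps to separate the effect of referral management from an outside event, such as a national contract or tariff change that falls at the same time.

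Sefton could sit steadily above or below the national figure for reasons that predate the system. Tested point by point, that would yield significant results with no differential change at all. Conversely, a list of significant and non-significant months gives no estimate of differential change with an interval. Repeated testing also produces chance findings, and a reader could take an isolated significant month as evidence for or against the intervention.

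**Working it through.** The protocol gives no error rate, significance level or sample size for this comparison, so there is no figure of its own to reproduce.

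**1. Number of tests.** The HES comparison is tied to the implementation period, months 12 to 36, which is 24 points if HES is monthly (assumption). Testing the whole series would give 12 + 24 = 36. If only the two implementation stages are meant, there are 2.

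**2. Chance of at least one false difference, independent tests.** With k tests at level α (0.05 assumed, two-sided, uncorrected) it is 1 − (1 − α)^k:

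- k = 24: 1 − 0.95^24 = 0.708, with 24 × 0.05 = 1.2 false positives expected
- k = 2: 1 − 0.95^2 = 0.0975
- k = 24 at α = 0.01: 1 − 0.99^24 = 0.214

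**3. Allowing for autocorrelation.** The protocol gives no size for it, so a range was simulated: stationary first-order autoregressive test statistics, 100,000 runs, α = 0.05, 24 points.

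| Autocorrelation | At least one false difference |
|---|---|
| 0 | 71% |
| 0.4 | 67% |
| 0.6 | 62% |
| 0.8 | 48% |
| 0.9 | 35% |

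**4. Constant offset, identical trends.** Let the Sefton-minus-national difference be a constant of 1 SD plus independent unit-variance noise. The chance that one month is flagged at 0.05 is Φ(−0.96) + Φ(−2.96) = 0.170. Over 24 months that gives 24 × 0.170 = 4.1 flagged months on average and a chance of at least one of 1 − 0.830^24 = 0.989.

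**5. Would a multiplicity rule cure this?** Bonferroni over 24 points uses α = 0.05/24 = 0.00208, critical value 3.078. With no offset, the familywise error is 1 − (1 − 0.00208)^24 = 0.049, as intended. With the offset and identical trends:

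- 1 SD: 1 − Φ(2.078) = 0.0189 per month, so 1 − 0.9811^24 = 0.37
- 2 SD: 1 − Φ(1.078) = 0.1405 per month, so 1 − 0.8595^24 = 0.97

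The correction handles chance findings, but the test still responds to the offset.

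**6. A test that matches the aim.** A joint F-test of level and slope changes at both interruptions was simulated on the difference series (36 months, independent errors, 4,000 runs). It rejected in 4.9% of runs with no offset and in 4.7% to 5.5% with offsets of 0.5 to 2 SD and no difference in trend. It therefore ignores a constant offset. These rates assume independent errors; with autocorrelated data the model must allow for it.

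**The case against.** The strongest reply is that the protocol does plan to compare trends. It says that pre/post effects at Sefton will be set against national trends, in the paragraph on time series regression, and then defines those effects as level and slope changes. The exact model could sit in an analysis plan that is not shown. This stands in part. A reader might infer that no comparison of trends is intended, and the text does not support that. But the protocol goes further than leaving the test open: it names one, and the one it names does not fit the intent.

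A reader might also infer that HES is the study's only protection against secular trends. The text does not support that either. The long two-stage series is named first, HES is added to it, and the principal analysis is Sefton's own interrupted time series. HES is, however, the only external comparator.

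Third, the number of tests is open. A recorded time point need not be a month: in section IX, the part on secondary care providers uses the term for the two implementation stages, though for observation visits and interviews. Monthly HES data, a level of 0.05 and the absence of correction are assumptions. It is tempting to quote the 84% that follows from 36 independent monthly tests (1 − 0.95^36 = 0.842), or to call a false finding almost certain. The first does not fit a comparison described for the implementation period, and the second does not survive autocorrelation of 0.8 or 0.9. Silence on multiplicity is not itself a fault in a protocol. None of this touches the mismatch between test and aim.

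**Conclusion.** The point holds as a mismatch between aim and test in a supportive analysis. The only significance test named for HES addresses differences at single points, whereas the stated aim concerns trends and pre/post effects. That conclusion needs no assumption about the number of tests or the significance level.

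The size of the added false-positive risk does depend on assumptions. With 24 monthly tests at 0.05, uncorrected, it runs from about 71% (independent) through 62% (autocorrelation 0.6) to 35% (0.9). It is about 21% at a level of 0.01 with independent tests, and about 10% if only two time points are tested at 0.05. The principal Sefton estimates are unaffected. This is a worthwhile, inexpensive correction and not a defect that undermines the study.

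**What to change.** In the closing paragraph of the quantitative analysis, delete the phrase on testing at each time point. In its place:

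- Fit one model to the monthly secondary-care series for Sefton and for the nation excluding Sefton, with series-by-level and series-by-slope terms at both interruptions and autocorrelated errors. Modelling the log of the Sefton-to-national ratio with the same breaks is an equivalent route.
- Report the difference in level change and in slope change at each interruption with 95% confidence intervals.
- Plot the monthly points for both series without tests.

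This extends the piecewise regression already planned. The wording change is small, but there are two practical conditions. The HES extract must be monthly and include the 12 baseline months; the protocol states neither. Hospital activity also lags referrals by the waiting time, so a break may appear later in HES than in the referral data. The analysis should therefore remain a supportive control analysis beside the referral-based one.
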